5.3.3 Treatment

On the day of the first scheduled Pan-HER infusion (C1/D1), and prior to the start of infusion (SOI), the Investigator must assess whether any changes have occurred in the clinical state of the patient, which would exclude the patient from the trial.

Pan-HER will be administered by IV infusion on either a Q1W or a Q2W schedule:

- Q1W: dosing will be every 7 (±2) days. Four (4) doses of Pan-HER administered Q1W constitute 1 cycle.
- Q2W: dosing will be every 14 (±2) days. Two (2) doses of Pan-HER administered Q2W constitute 1 cycle.

Patients in Part 1 will be enrolled to either Q1W or Q2W dose-escalation cohorts until establishment of an MAD, an MTD, and/or a RP2D for each schedule.

During Part 2, all patients will receive the RP2D and regimen of Pan-HER.

For all patients, the dose and schedule to be administered will be documented on the Screening and Allocation Form. Patients will receive the allocated dose and schedule according to their cohort assignment until treatment withdrawal. There will be no intra-patient dose-escalation. Dose-delays of Pan-HER and/or intra-patient dose-reduction(s) may be required upon occurrence of specific toxicities, as described in **Section 7.1.4**.

Treatment will continue until unacceptable toxicity or other conditions preventing further treatment, progressive disease (PD), termination of the trial, or patient's decision to withdraw.

Disease status evaluation will be by computed tomography (CT) or magnetic resonance imaging (MRI) according to Response Evaluation Criteria in Solid Tumors (Version 1.1) (RECIST v1.1) (22).

Confidential Page 41 of 156

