In the initial portion of dose-escalation, patients will be sequentially enrolled to single-patient cohorts of increasing doses of Pan-HER. One patient will be treated at each dose level until the occurrence of a toxicity* during Cycle 1 that activates the stopping rule of the single-patient cohort titration design. The cohort will expand to 3 patients and the design switch to a classical 3+3 dose-escalation design.

*Grade 2 toxicity, assessed by the Investigator as possibly, probably, or related to Pan-HER with the exception of Grade 2 alopecia, nausea, anemia, lymphopenia, and/or eosinophilia. Toxicity grading will be according to the CTCAE v4.03.

If a toxicity that activates the stopping rule of the single-patient cohort design has not occurred in the first 3 cohorts (i.e., 1 mg/kg, 2 mg/kg, and 4 mg/kg), the next cohort to open will be a 3-patient cohort and the design will switch to the 3+3 design.

Confidential Page 57 of 156

^{*}Mandatory intensive IRR and oropharyngeal mucositis prophylaxis; 4-hour infusion (designated "P")

Note: The transition from single patient cohorts to 3+3 dose-escalation design occurred beginning with Dose Level 3 (4 mg/kg Q1W). All Dose Levels evaluated thereafter are to be comprised of a minimum of 3 patients.

Each patient enrolled will receive Pan-HER at the allocated dose and schedule, unless dose-reduction is necessary as specified in **Section 7.1.4**. There will be no intra-patient dose-escalation.

The SMC will review safety data and make decisions regarding the advisability of continuing accrual to a particular dose cohort, and dose-escalation and accrual of patients to a higher dose cohort.

Classical 3+3 Dose-Escalation Design

During the 3+3 design portion of dose-escalation, at least 3 patients will be treated per dose level.

Staggered Dosing: Enrollment will be staggered between the first and second patient in each new dose level tested. The first patient must have completed and tolerated the first 2 doses of Pan-HER with Q1W dosing, or the first dose of Pan-HER with Q2W dosing, including follow-up until Day 15 of Cycle 1 (C1/D15) in order to allow for review of clinical and laboratory assessments. Thereafter patients within a cohort may be added concurrently.

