Each patient enrolled will receive Pan-HER at the allocated dose and schedule, unless dose-reduction is necessary as specified in **Section 7.1.4**. There will be no intra-patient dose-escalation.

During Part 1, intermediate dose level(s) between 2 planned dose levels may be evaluated to further characterize safety and tolerability of Pan-HER, if indicated based on toxicity observations and/or results from PK and/or target engagement analyses.

The SMC will review safety data and make decisions regarding the advisability of continuing accrual to a particular dose cohort, dose-escalation and accrual of patients to a higher dose cohort, and the RP2D to be used in Part 2.

RP2D: The RP2D may include a dose or a combination of doses equal to or lower than the MTD for the Q1W and/ or Q2W dosing regimens. A dose or doses between tolerated doses investigated in Part 1 may also be selected if data indicate this to be optimal. Furthermore, the RP2D and regimen ultimately identified for use in Part 2 of this trial may be a dose or a combination of doses to be administered on a Q1W schedule, a Q2W schedule, or a combination thereof. The selection will be based on tolerability demonstrated with Q1W and Q2W dosing, as well as available PK and target engagement results, as applicable.

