7.1.3.6 Infusion-Related Reactions to Pan-HER

An IRR is defined as an AE occurring during the Pan-HER infusion and up to 2 hours after the end of infusion (EOI), which is assessed by the Investigator as possibly, probably, or related to Pan-HER. Signs of IRRs may include but are not limited to facial flushing and swelling, shortness of breath, headache, diaphoresis, tachycardia, hypotension, chills, rigors, chest and throat tightness, as well as chest, back and/or abdominal discomfort.

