	Patient will either be discontinued from further treatment or receive subsequent treatments at a reduced dose (if >6 hours in duration); if treatment is continued administer subsequent infusions during Cycle 1 at 50% of the prior rate
	Thereafter, if vital signs remain stable and symptoms do not recur, at the discretion of the Investigator an attempt may be made to slowly increase the rate of infusion. Final infusion duration should not be briefer than the initial rate attempted in the patient.
Grade 4	Discontinue infusion
Life-threatening consequences; urgent intervention indicated	 Administer necessary life-support measures, as indicated Discontinue from further treatment
	Discontinue from further treatment

Abbreviations (in alphabetical order): CTCAE, Common Terminology Criteria for Adverse Events v4.03; h, hours; IV, intravenous; ; NSAID, nonsteroidal anti-inflammatory drug

Confidential Page 63 of 156

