7.1.4.3 Dose-Reduction for Pan-HER-Related Toxicities

Patients experiencing any of the following toxicities, assessed as possibly, probably, or related to Pan-HER, will have their dose reduced in accordance with the reduction schedule outlined in **Table 9**:

- 1. Grade 3 non-hematologic toxicity regardless of duration, with the exception of:
 - a. Grade 3 nausea, vomiting, diarrhea, or fatigue lasting ≤2 days with best supportive care
 - b. Grade 3 asymptomatic electrolyte abnormality that is not considered clinically significant by the Investigator and that is controlled with medical therapy
- 2. Grade 4 non-hematologic toxicity, with the exception of:
 - a. Grade 4 asymptomatic electrolyte abnormalities that is not considered clinically significant by the Investigator and that is controlled with medical therapy
- 3. Neutropenia that is:
 - a. Grade 3-4 febrile neutropenia
 - b. Grade 4 and sustained (i.e., ANC $< 0.5 \times 10^9 / L [500 / mm^3]$, duration > 5 days)
- 4. Thrombocytopenia that is
 - a. Grade 3 with clinically significant hemorrhage
 - b. Grade 4 (platelets $<25 \times 10^9/L$ [25,000/mm³])
- 5. AST/ALT elevation >3×ULN (or >3× baseline if elevated at study entry due to hepatic involvement by tumor) with bilirubin elevation >2×ULN without evidence of cholestasis that cannot be explained by factors not related to Pan-HER
- 6. Evidence of cardiac toxicity as defined by either:
 - a. ≥16% absolute decrease in LVEF from baseline, or
 - b. LVEF below the institutional lower limit of normal and ≥10% absolute decrease in LVEF from baseline

Need for more than three dose-reductions of Pan-HER will lead to withdrawal from treatment.

Confidential Page 65 of 156

Table 9	Pan_HER	Dose-Reduction	n Schedule
1 41711 /			,,,,,,,,,,,,,,,,,,,,,,,,,,,,,,,,,,,,,,,

Dose Level	First Reduction	Second Reduction	Third Reduction
Dose level 1 1.0 mg/kg	0.5 mg/kg	0.25 mg/kg	0.125 mg/kg
Dose level 2	1 mg/kg	0.5 mg/kg	0.25 mg/kg
Dose level 3	Dose level 2	1 mg/kg	0.5 mg/kg
Dose level 4	Dose level 3	Dose level 2	1 mg/kg
Continue as above	Next lower tolerated dose	Next lower tolerated dose	Next lower tolerated dose

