Dose-reductions will be to the next lower tolerated dose (one level per dose-reduction step). If dose-reduction below a previously tested dose level is warranted, the dose will be reduced by 50% (i.e., to ½ the previous dose) in any subsequent stepwise reduction(s). Need for more than three dose-reductions of Pan-HER will lead to withdrawal from treatment.

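### Table 8 ties the dose reduction after a Grade 3 infusion reaction to a duration above 6 hours, while Section 7.1.4.3 requires it at any duration

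*Protocol*

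**What the plan says.** Two places in the protocol deal with the dose after a Grade 3 IRR.

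- **Protocol 7.1.3.7, Table 8, Grade 3 row.** The infusion is stopped and not resumed. The patient will then either come off treatment or "receive subsequent treatments at a reduced dose (if >6 hours in duration"). The row goes on to say that, if treatment continues, the remaining Cycle 1 infusions run at half the previous rate. The text above the table presents it as recommended guidance and leaves room for clinical judgment.
- **Protocol 7.1.4.3.** Patients with any listed related toxicity "will have their dose reduced in accordance with the reduction schedule outlined in" Table 9. The first listed toxicity is "Grade 3 non-hematologic toxicity regardless of duration, with the exception of" two items: nausea, vomiting, diarrhea or fatigue that settles within two days under supportive care, and controlled asymptomatic electrolyte changes judged not clinically significant. The text under Table 9 adds: "Dose-reductions will be to the next lower tolerated dose (one level per dose-reduction step").

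Sections 5.3.3 and 7.1.3.2 both refer to Section 7.1.4 for reductions. Section 5.3.3 says "intra-patient dose-reduction(s) may be required upon occurrence of specific toxicities, as described in" Section 7.1.4, and Section 7.1.3.2 says "Each patient enrolled will receive Pan-HER at the allocated dose and schedule, unless dose-reduction is necessary as specified in" the same section.

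**The concern.** The two rules give different instructions for one group: patients who continue after a Grade 3 IRR lasting 6 hours or less. Section 7.1.4.3 requires a lower dose for them. Table 8 attaches its reduction to reactions above 6 hours and, for a shorter reaction with continued treatment, states only a slower rate.

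Table 8 is the table a site would consult after an infusion reaction, and its Grade 3 row is written as an instruction rather than a suggestion. A site working from it could give the full assigned dose to someone who has just had a severe infusion reaction, contrary to the binding rule.

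**Working it through.** **Step 1. Does a Grade 3 IRR fall under 7.1.4.3?**

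- Causality: Section 7.1.3.6 defines an IRR as an adverse event "which is assessed by the Investigator as possibly, probably, or related to Pan-HER". That is the causality threshold 7.1.4.3 uses, so every IRR meets it.
- Type and grade: a Grade 3 IRR is a Grade 3 non-hematologic toxicity.
- Exceptions: neither Grade 3 exception covers an IRR.

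So 7.1.4.3 applies to every Grade 3 IRR, whatever its duration.

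**Step 2. The two rules side by side, for a patient who continues treatment**

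| Duration of Grade 3 IRR | Table 8 | Section 7.1.4.3 | Result |
|---|---|---|---|
| Above 6 hours | Reduced dose | Reduced dose | Agree |
| 6 hours or less | No reduction stated | Reduced dose | Conflict |

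Without the parenthetical, both rows agree.

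**Step 3. Which text should give way?** Sections 5.3.3 and 7.1.3.2 make Section 7.1.4 the place that specifies reductions, and 7.1.4.3 is mandatory where Table 8 is advisory. DLT criterion 1 in Section 9.5.1 also has no duration limit and no IRR exception. The Amendment 1 entry in the summary of changes points the same way: it removed, from both 7.1.4.3 and 9.5.1, an exception for Grade 3 IRRs resolving within 6 hours. The conflict lies within the current text; the log only supports the direction of the correction.

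**Step 4. Size of the reduction at issue.** The plan gives no figure to reproduce. Inputs are the dose levels in Section 7.1.3.2 and the steps in Table 9. Table 9 lists the first reduction for Dose Levels 1 to 4. Above those it says only that the next lower tolerated dose is used, so for 9 mg/kg and higher I assume that this is the adjacent planned level.

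- Reduction = (current − next lower) / current
- Excess of a full re-dose over the required dose = current / next lower − 1

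| Current → next lower (mg/kg) | Reduction | Excess if full dose is given | Basis |
|---|---|---|---|
| 1 → 0.5 | 0.5/1 = 50% | 1/0.5 − 1 = 100% | Table 9 |
| 2 → 1 | 1/2 = 50% | 2/1 − 1 = 100% | Table 9 |
| 4 → 2 | 2/4 = 50% | 4/2 − 1 = 100% | Table 9 |
| 6 → 4 | 2/6 = 33% | 6/4 − 1 = 50% | Table 9 |
| 9 → 6 | 3/9 = 33% | 9/6 − 1 = 50% | Assumed |
| 12 → 9 | 3/12 = 25% | 12/9 − 1 = 33% | Assumed |
| 15 → 12 | 3/15 = 20% | 15/12 − 1 = 25% | Assumed |
| 18 → 15 | 3/18 = 17% | 18/15 − 1 = 20% | Assumed |

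These are mg/kg per infusion and take no account of schedule. The lower rows of the dose range stay relevant because Section 7.1.3.2 allows Q1W doses below 6 mg/kg to be explored with prophylaxis.

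**Step 5. Effect on the primary endpoint.** A related Grade 3 IRR in Cycle 1 is already a DLT under 9.5.1. A patient who fails to complete Cycle 1 because of drug toxicity stays in the DLT Analysis Set (Section 10.2). A reduction within Cycle 1 means the observation period was not completed at the assigned dose (Section 9.5.2), but that follows from applying 7.1.4.3 correctly. Neither the DLT count nor the MTD depends on which rule the site follows.

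**The case against.** The strongest reply is that the protocol already resolves the matter. Table 8 is guidance subject to clinical judgment, 7.1.4.3 is mandatory, and a site that reads the whole protocol will reduce the dose. Table 8 also never offers full-dose re-treatment. For a shorter reaction it could be read as silent, leaving 7.1.4.3 to apply, or as allowing only discontinuation, which is more cautious. There are safeguards too: Grade 2 or higher IRRs and presumed DLTs go to the sponsor within 24 hours (Sections 9.6 and 9.5.3), and the safety committee reviews the data regularly (Section 12.1).

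Part of this stands. Table 8 does not expressly authorize a full dose, the safeguards make an unnoticed error less likely, and the percentages in Step 4 describe the dose difference, not how often it would arise or what harm would follow.

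It does not remove the conflict. Whether the row is read as silent or as discontinuation only, it is out of line with a rule that prescribes a reduction. The row goes on to address continued treatment, so a site can reasonably look there for the dose. Clinical judgment in managing a reaction does not waive 7.1.4.3, and Section 17 allows no protocol waivers.

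**Conclusion.** The concern holds and is minor. For continuing patients with a Grade 3 IRR of 6 hours or less, Table 8 omits a reduction that 7.1.4.3 requires. Table 8 is wrong as written, because 7.1.4.3 sits in the section the protocol names for reductions. A full re-dose would exceed the required dose by 20% to 100%, depending on level; the figures from 9 mg/kg upward rest on the adjacent-level assumption.

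No patient is documented as dosed under the conflict. The one Grade 3 IRR reported as of Amendment 6, among 19 patients entered, led to discontinuation (Protocol 3.2.4.1), and enrollment was later stopped during Part 1 (SAP Section 1). The point matters for any continued treatment under this protocol or reuse of the IRR table.

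**What to change.** Delete the duration parenthetical from the Grade 3 row of Table 8 and, optionally, add a cross-reference to Section 7.1.4.3 and Table 9. Any patient who continues after a Grade 3 IRR then receives a reduced dose, and the option to discontinue stays. Leave 7.1.4.3, 9.5.1 and the SAP definition of DLT as they are. The cost is one parenthetical in one table row, with no change to sample size, DLT rules or analysis.

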7.1.4 Dose Adjustment and Delays of Pan-HER

The dose of Pan-HER in mg/kg assigned to the individual patient, will be confirmed by the Sponsor or designee prior to C1/D1.

Based on the body weight of the patient, the trial site will calculate the nominal dose of Pan-HER to be administered in mg.

Weight changes ($\geq \pm 10\%$) for a patient during trial should be accompanied by recalculation of the dose (Section 7.1.4.1).

Furthermore, dose-delays of Pan-HER and intra-patient dose-reduction(s) may also be required upon occurrence of specific toxicities (Section 7.1.4.2).

7.1.4.1 Dose-Adjustment for Body Weight

Pan-HER is dosed in mg/kg and the dose to be administered will be calculated based on the actual body weight of the patient. The dose calculated may be used for subsequent infusions, unless body weight changes of $\geq \pm 10\%$, in which case the dose should be adjusted according to the change in body weight. Recalculation for lower weight changes is allowed if required by trial site standard practices.

7.1.4.2 Dose-Delays for Pan-HER-Related or Disease-Related Toxicities

Clinical judgment will be used when determining whether it is advisable to continue a patient on to the next dosing. In order to dose a patient, the following retreatment criteria must be met. Evaluations must occur at minimum prior to each Cycle 1 dose and prior to D1 and D15 doses each cycle thereafter:

- 1. ANC $> 1.5 \times 10^9 / L (1500 / mm^3)$
- 2. Platelet count >75 $\times 10^9$ /L (75,000/mm³)
- 3. Any ongoing AEs should NOT meet the criteria for DLT, during the DLT-observation period
- 4. Any ongoing AEs, assessed as possibly, probably, or related to Pan-HER, should have either ameliorated to ≤ Grade 1 severity, returned to baseline status, or resolved with the exception of Grade 2 clinical events that are being adequately controlled with best supportive care (e.g., nausea, vomiting, diarrhea, fatigue) and asymptomatic laboratory abnormalities that are considered clinically insignificant or that are resolving with medical therapy

Should any one of the criteria above not be met, dosing of Pan-HER must be delayed until the patient meets the above criteria. All per protocol assessments must be done.

Confidential Page 64 of 156

7.1.4.3 Dose-Reduction for Pan-HER-Related Toxicities

Patients experiencing any of the following toxicities, assessed as possibly, probably, or related to Pan-HER, will have their dose reduced in accordance with the reduction schedule outlined in **Table 9**:

- 1. Grade 3 non-hematologic toxicity regardless of duration, with the exception of:
 - a. Grade 3 nausea, vomiting, diarrhea, or fatigue lasting ≤2 days with best supportive care
 - b. Grade 3 asymptomatic electrolyte abnormality that is not considered clinically significant by the Investigator and that is controlled with medical therapy
- 2. Grade 4 non-hematologic toxicity, with the exception of:
 - a. Grade 4 asymptomatic electrolyte abnormalities that is not considered clinically significant by the Investigator and that is controlled with medical therapy
- 3. Neutropenia that is:
 - a. Grade 3-4 febrile neutropenia
 - b. Grade 4 and sustained (i.e., ANC $< 0.5 \times 10^9 / L [500 / mm^3]$, duration > 5 days)
- 4. Thrombocytopenia that is
 - a. Grade 3 with clinically significant hemorrhage
 - b. Grade 4 (platelets $<25 \times 10^9/L$ [25,000/mm³])
- 5. AST/ALT elevation >3×ULN (or >3× baseline if elevated at study entry due to hepatic involvement by tumor) with bilirubin elevation >2×ULN without evidence of cholestasis that cannot be explained by factors not related to Pan-HER
- 6. Evidence of cardiac toxicity as defined by either:
 - a. ≥16% absolute decrease in LVEF from baseline, or
 - b. LVEF below the institutional lower limit of normal and ≥10% absolute decrease in LVEF from baseline

Need for more than three dose-reductions of Pan-HER will lead to withdrawal from treatment.

Confidential Page 65 of 156

Table 9	Pan_HER	Dose-Reduction	n Schedule
1 41711 /			,,,,,,,,,,,,,,,,,,,,,,,,,,,,,,,,,,,,,,,

Dose Level	First Reduction	Second Reduction	Third Reduction
Dose level 1 1.0 mg/kg	0.5 mg/kg	0.25 mg/kg	0.125 mg/kg
Dose level 2	1 mg/kg	0.5 mg/kg	0.25 mg/kg
Dose level 3	Dose level 2	1 mg/kg	0.5 mg/kg
Dose level 4	Dose level 3	Dose level 2	1 mg/kg
Continue as above	Next lower tolerated dose	Next lower tolerated dose	Next lower tolerated dose

Dose-reductions will be to the next lower tolerated dose (one level per dose-reduction step). If dose-reduction below a previously tested dose level is warranted, the dose will be reduced by 50% (i.e., to ½ the previous dose) in any subsequent stepwise reduction(s). Need for more than three dose-reductions of Pan-HER will lead to withdrawal from treatment.

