6.3.1 Withdrawal from Treatment

The patient must be withdrawn from treatment with Pan-HER in the event of any of the following:

- A DLT considered by the Investigator to require treatment discontinuation (Part 1 only) (See **Section 9.5**)
- Occurrence of an AE considered by the Investigator to require treatment discontinuation
- Need for more than three dose-reductions of Pan-HER
- Patients with hepatotoxicity that cannot be explained by factors not related to Pan-HER, i.e., Hy's Law criteria (24)

Note: Patients meeting all three of the following are considered to have met Hy's Law criteria:

- Hepatocellular injury, generally shown by a higher incidence of 3-fold or greater elevations above ULN of ALT or AST (or > 3 × baseline if elevated at study entry due to hepatic involvement by tumor).
- Elevation of serum total bilirubin to $\ge 2 \times ULN$, without findings of cholestasis (elevated serum alkaline phosphatase [ALP] $< 2 \times ULN$).
- No other reason to explain the combination of increased aminotransferase and serum total bilirubin, such as viral hepatitis A, B, or C; preexisting or acute liver disease; or another drug capable of causing the observed injury.
- PD, verified by CT/MRI according to RECIST v1.1
- Treatment failure not meeting the criteria for PD, but considered by the Investigator to require treatment discontinuation
- Requirement for a significant surgical procedure

Note: Patients requiring a minor surgical procedure (e.g., port placement, skin abscess drainage) may continue at the Investigator's discretion following discussion with the Sponsor or designee. A brief interruption in therapy may be considered.

Confidential Page 52 of 156

- An intercurrent illness which, in the opinion of the Investigator, would prevent completion of trial-related evaluations
- Use of prohibited concomitant medication, as defined in **Section 7.5.2**
- Pregnancy
- Significant deviation from the eligibility criteria may require discontinuation after discussion with the Sponsor
- Noncompliance with trial procedures may require discontinuation after discussion with the Sponsor
- Patient election to discontinue treatment
- Termination of the trial by the Sponsor

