7.1.3.7 Handling of Infusion-Related Reactions to Pan-HER

Recommended guidelines for management of IRRs are shown in **Table 8**. In all cases, the Investigator should use best clinical judgment in managing such reactions.

Confidential Page 62 of 156

Table 8 Infusion-Related Reactions Management Guidelines

CTCAE Grade	Management/Treatment
Grade 1	Continue infusion; consider slowing to 50% of the prior rate
Mild transient reaction;	Monitor closely
infusion interruption not indicated; intervention not indicated	If infusion is extended, administer subsequent infusions during Cycle 1 at the prolonged rate
	Thereafter, if vital signs remain stable and symptoms do not recur, at the discretion of the Investigator an attempt may be made to slowly increase the rate of infusion. Final infusion duration should not be briefer than the initial rate attempted in the patient
Grade 2	Interrupt infusion for a minimum of 30 minutes
Therapy or infusion interruption indicated but responds promptly to symptomatic treatment (e.g., antihistamines, NSAIDs, narcotics, IV	Administer symptomatic treatment (e.g., antihistamines, NSAIDs, etc.) and appropriate supportive care (e.g., bronchodilator, oxygen, etc.), as indicated
fluids); prophylactic medications indicated for ≤ 24 h	• When symptoms have resolved or decreased to Grade 1, restart infusion at 50% of the prior rate
	Monitor closely
	If symptoms recur, stop the infusion, institute remedial therapy, monitor closely and evaluate whether the patient can continue the trial
	Administer subsequent infusions during Cycle 1 at the prolonged rate
	Thereafter, if vital signs remain stable and symptoms do not recur, at the discretion of the Investigator an attempt may be made to slowly increase the rate of infusion. Final infusion duration should not be briefer than the initial rate attempted in the patient
Grade 3	Discontinue the infusion
Prolonged (e.g., not rapidly responsive to symptomatic medication and/or brief interruption of infusion); recurrence of symptoms following initial improvement;	Administer symptomatic treatment (e.g., antihistamines, NSAIDs, glucocorticoid etc.) and appropriate supportive care (e.g., bronchodilator, oxygen, IV fluid etc.), as indicated
hospitalization indicated for clinical sequelae	Do not resume infusion

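### For a Grade 4 infusion-related reaction, Protocol 7.1.4.3 directs a dose reduction while Table 8 recommends discontinuation, and no binding text settles which applies (low priority)

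*Protocol*

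**What the plan says.** Four parts of the protocol bear on what happens after a Grade 4 IRR.

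- **Section 7.1.3.6** defines an IRR as an adverse event during the infusion or within 2 hours of its end "which is assessed by the Investigator as possibly, probably, or related to Pan-HER".
- **Section 7.1.4.3** states that patients with any listed related toxicity "will have their dose reduced in accordance with the reduction schedule outlined in" Table 9. Item 2 of the list reads "Grade 4 non-hematologic toxicity, with the exception of" one entry: an asymptomatic electrolyte abnormality that is not clinically significant and is controlled with treatment.
- **Section 7.1.3.7, Table 8**, in its Grade 4 row, says "Discontinue from further treatment". The section introduces the table with "Recommended guidelines for management of IRRs are shown in" Table 8, and adds "In all cases, the Investigator should use best clinical judgment in managing such reactions". The synopsis also describes the IRR guidance as recommended.
- **Section 6.3.1** lists the events for which withdrawal is mandatory. A Grade 4 IRR is not named. It can enter through "Occurrence of an AE considered by the Investigator to require treatment discontinuation", or through the matching entry for a DLT, which carries the same condition.

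**The concern.** A Grade 4 IRR is a life-threatening reaction to the study drug. A site looking up what to do next finds a directive (*will*) to reduce the dose in one section and a recommendation to stop for good in another. The safer instruction is the weaker in form. Giving a reduced dose after such a reaction would therefore breach no mandatory rule, and taken literally 7.1.4.3 would call for it. What is at stake is the safety of an individual patient and the clarity of the instruction to sites. No estimate or decision rule is involved.

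**Working it through.** The plan attaches no figure to this point, so the check is to trace one Grade 4 IRR through each section.

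1. **Is it related?** Yes, by the definition in 7.1.3.6. The three causality categories there are the same three that trigger 7.1.4.3.
2. **Does 7.1.4.3 item 2 apply?** Yes. An IRR is non-hematologic, and the single exception (controlled, asymptomatic electrolyte abnormality) does not fit it. Result: reduce the dose per Table 9.
3. **What does Table 8 say?** Discontinue, with no alternative. The Grade 3 row differs: "Patient will either be discontinued from further treatment or receive subsequent treatments at a reduced dose". The table thus separates the grades deliberately, and at Grade 4 leaves out the reduced dose. Result: discontinue, as guidance subject to clinical judgment.
4. **Does 6.3.1 bind?** Only once the Investigator decides that the event requires discontinuation. Result: conditional withdrawal.
5. **Do the retreatment criteria in 7.1.4.2 block the next dose?** Only until the event has ameliorated or resolved. An acute reaction can meet that condition before the next scheduled dose. Result: a delay, not a bar.
6. **Is there a precedence rule?** None was found in 6.3.1, 7.1.3.7, 7.1.4 to 7.1.4.3, 9.5.1 or the synopsis.

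The outcome is one unconditional directive (reduce), one recommendation (discontinue), one conditional requirement (withdraw) and one temporary hold.

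**Effect on the primary endpoint.** Under 9.5.1 item 2, a related Grade 4 non-hematologic toxicity in the DLT observation period is a DLT whether or not the patient is dosed again. The DLT Analysis Set (Protocol 10.2, SAP 4.5) drops only patients who fail to complete Cycle 1 for reasons other than drug toxicity, so a patient withdrawn for a Grade 4 IRR stays in. The DLT count is the same under either instruction.

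**Reported experience (Protocol 3.2.4.1).** Patients with an IRR: 2 at 4 mg/kg Q1W + 2 at 6 mg/kg Q2W + 3 at 9 mg/kg Q2W = 7 of 16, the total given there. Adding 1 at 9 mg/kg Q2W with prophylaxis gives 8 of 19. One was Grade 3, the other 7 were Grade 1 or 2, and none was Grade 4. The documents give no IRR counts after Amendment 6.

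**The case against.** The strongest reply is that the sections can be read together. Section 7.1.4.3 is a general rule on what dose to give if dosing continues, whereas Table 8 is the specific IRR instruction and its Grade 4 row is imperative with one option. Section 7.1.4 says only that reductions may be required, 7.1.4.2 leaves the next dose to clinical judgment, and 6.3.1 makes withdrawal mandatory once the Investigator finds it necessary. Being listed in 7.1.4.3 also need not mean reduction instead of withdrawal: item 5 there largely overlaps the Hy's Law criteria, for which 6.3.1 mandates withdrawal. In practice, the one reported Grade 3 IRR patient was discontinued, IRRs of Grade 2 or higher must reach the sponsor within 24 hours (9.6), and the safety monitoring committee reviews safety data (12.1).

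Most of this stands, and it is why the point is minor. What it does not supply is a rule. The liver example shows the gap: 6.3.1 names Hy's Law cases and so settles the overlap with item 5, but it does not do the same for a Grade 4 IRR.

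Three stronger inferences are tempting, and the documents do not support them.

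- *That the protocol forces re-exposure after a life-threatening reaction.* It does not; the provisions just listed let the Investigator stop at any time.
- *That the early IRR counts measure the size of the defect.* They describe how often reactions occurred, not how likely an Investigator is to dose again after a Grade 4 event.
- *That the Amendment 1 log shows item 2 was written with Grade 4 IRRs in mind.* The exception it removed concerned only transient Grade 3 IRRs, and it is superseded text.

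A mismatch also exists at Grade 3, but of a milder kind: reduction is one of the two courses that Table 8 offers there, so the instructions are not opposed.

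**Conclusion.** The inconsistency is real and small. For a Grade 4 IRR, the directive in 7.1.4.3 item 2 and the recommendation in Table 8 differ, the safer one is not binding, and nothing ranks them. The conclusion rests on the plain reading that a Grade 4 IRR is a related non-hematologic toxicity. The view that most investigators would discontinue anyway is a judgment, based on Table 8 being the more specific text.

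DLT counting, sample size and the planned analyses are unaffected. Practical reach is narrow, because enrollment was stopped in Part 1 and Part 2 did not take place (SAP 1 and 4.14). The point matters only for any patients still on treatment under Protocol 5.6, for a rollover protocol, or if this text is reused. Low priority.

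**What to change.** Make two short wording changes:

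1. In 6.3.1, add Grade 4 IRR to the list of events that require withdrawal from treatment.
2. In 7.1.4.3 item 2, except Grade 4 IRR, with a cross-reference to 6.3.1 and Table 8.

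The first change supplies the binding rule and the second removes the contrary directive. With both in place, no separate precedence sentence is needed in 7.1.3.7.

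Protocol 17 requires sponsor agreement and prior written approval from the health authority and the IRB/EC. The point does not justify an amendment of its own, so the changes should travel with the next amendment, if there is one, and be carried into any rollover or reused protocol. They add no visit, procedure or data item and do not touch the SAP. The only thing lost is the Investigator's option to continue dosing after a Grade 4 IRR, which Table 8 already advises against.
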